#### **16.1.5.2.3. Vital Signs**

Changes from baseline will be summarized for all vital signs by dose levels. A separate summary will be presented for incidence of clinically significant changes from baseline.

#### **16.1.5.2.4. Columbia Suicide Severity Rating Scale**

C-SSRS data will be summarized by dose level using descriptive statistics (number of participants, mean, SD, median, minimum, and maximum) for continuous variables, and using frequency and percentage for discrete variables.

#### **16.1.5.2.5. Physical Examinations**

The changes from baseline will be summarized by dose level.

#### **16.1.5.2.6. Limited Neurological Examinations**

The changes from baseline in the limited neurological examination (MMSE, cranial nerves, coordination/cerebellar function, motor and reflexes) will be summarized by dose level.

#### **16.1.5.2.7. Electrocardiogram**

The changes from baseline will be summarized using shift tables. The number and percentage of participants with shifts to the categorical values (abnormal not AE, or abnormal and AE) will be summarized by dose level.

### **16.1.6. Antigenicity/Immunogenicity Data**

#### **16.1.6.1. Analysis Population**

The analysis population for immunogenicity is defined as all participants who receive at least 1 dose of study treatment and have at least 1 postdose immunogenicity sample collected.

#### **16.1.6.2. Methods of Analysis**

Results will be summarized by dose level.

### **16.1.7. Interim Analyses**

In Part A (SAD) of the study, CRM will be used as supporting evidence for continuous assessment of MTD for dose escalation decisions. In Part B (MAD) of the study, in addition to the safety review (blinded), a designated team of staff will review the available unblinded but de-identified PD and/or biomarker data (e.g., levels of total SOD1 protein and pNfH) from all previous cohorts at the completion of the last Day 106 visit of each cohort to determine whether to proceed with the subsequent planned dose cohorts. An interim analysis of key safety, secondary, and exploratory endpoints may be conducted based on data up to the 60-mg and/or

CONFIDENTIAL

The information contained herein may not be used, disclosed, or published without the written consent of  
Biogen MA Inc.

100-mg dose cohort to allow for the planning of the pivotal efficacy and safety study. The participants, investigative staff, and sponsor's staff responsible for site monitoring and data management will remain blinded to treatment assignment during the ongoing data review, as well as during interim analyses, to minimize the potential for bias in the data cleaning process. Details of the interim analysis will be provided in a separate statistical analysis plan.

### **16.1.8. Sample Size Considerations**

The maximum sample size of 36 participants for Part A of the study (SAD) is based on clinical rather than statistical considerations. Participants will be randomized to receive BIIB067 or placebo in a 3:1 ratio in each cohort. Each cohort will have a minimum of 4 participants (3 active and 1 placebo), and a maximum of 12 participants (9 active and 3 placebo). The final number for each cohort will be dependent on the DLT profile. If no DLT occurs in any dose level, then a total of 20 participants (15 active and 5 placebo) will be randomized. This design will allow for adequate evaluation of the safety of BIIB067, should DLT be encountered, as well as minimize participant exposure at subtherapeutic single doses.

For Part B (MAD), up to 48 participants will be enrolled in up to 4 cohorts, with up to 9 participants randomized to receive BIIB067 and 3 participants randomized to receive placebo for each cohort. This design will provide approximately 80% power to detect a difference in total SOD1 protein reduction between 25% from the BIIB067 group and 12% from the placebo group at a 10% significance level. The sample size calculation assumes the same 10.5% SD in the 2 treatment groups.

## **16.2. Part C**

The ITT population is defined as all participants who are randomized and receive at least 1 dose of study treatment.

### **16.2.1. Clinical Function**

#### **16.2.1.1. Analysis Population**

The primary analyses of clinical function will be evaluated in the mITT population (see Section 8.2.1 for definition) comprising the subset of the population who meet prognostic enrichment criteria for rapid disease progression who are randomized and receive at least 1 dose of study treatment. The primary analysis population will comprise participants who meet prognostic enrichment criteria for rapid disease progression to enable detection of a statistically significant and clinically meaningful treatment effect on clinical function over the 6-month treatment duration. The treatment effect of clinical function endpoints in the non-mITT population will be analyzed, where relevant, with nominal p-values presented. The clinical function data in the overall ITT population will be summarized and analyzed where relevant.

#### **16.2.1.2. Methods of Analysis**

##### **16.2.1.2.1. Analysis of the Primary Efficacy Endpoint**

The primary efficacy endpoint is the change from baseline to Week 28 in the ALSFRS-R total score, which will be analyzed as follows, depending on 2 scenarios:

CONFIDENTIAL

The information contained herein may not be used, disclosed, or published without the written consent of  
Biogen MA Inc.

1. If the number of deaths across both treatment arms is  $\geq 3$  (i.e.,  $\geq 5\%$  deaths out of a total of 60 patients in the mITT population), the JRT methodology to account for mortality [Berry 2013] will be used for the primary inference. When implementing the JRT methodology, MI will be used to handle withdrawals. The estimates will be obtained from an ANCOVA for change from baseline in ALSFRS-R at Week 28 with missing data imputed using MI. The corresponding nominal p-value from the ANCOVA will be presented as a sensitivity analysis.
2. If the number of deaths is  $< 3$  (i.e.,  $< 5\%$  deaths out of a total of 60 patients in the mITT population), ANCOVA with MI will be used as the primary analysis method for both inference and estimates. The p-value from the JRT will be presented as a sensitivity analysis.

The primary estimand is described as follows:

The primary analysis for the primary endpoint is the composite estimand [ICH 2017]. The estimand of the primary analysis is defined as follows:

- Population: all participants in the mITT population.
- Variable: change from baseline to Day 197 in the ALSFRS-R total score.
- Handling of intercurrent events: Relevant intercurrent events are handled using a composite strategy in which participants who have these intercurrent events are ranked against each other and against participants without any intercurrent event using the joint rank methodology based on MI datasets. The relevant intercurrent events are deaths and withdrawals. These participants will be handled using the composite strategy and ranked as described in this section. For withdrawals, this will be based on the imputed value for Day 197 from the MI datasets.
- Summary statistics: difference between treatment groups in least square means of Day 197 change from baseline with corresponding standard errors and 95% confidence intervals taken from the ANCOVA for change from baseline to Day 197, based on the MI datasets. The ANCOVA model will include treatment group as a fixed effect and covariates for ALSFRS-R total score, baseline disease duration since symptom onset, and use of riluzole or edaravone.

For the JRT analysis, the ranked scores will be analyzed for each of the 100 MI-complete datasets using an ANCOVA model with treatment included as a fixed effect and adjusted for the following covariates: baseline disease duration since symptom onset, baseline ALSFRS-R total score, and use of riluzole or edaravone. The p-value will be based on combining the estimates for the treatment differences using PROC MIANALYZE. The difference between treatment groups in median changes from baseline to each visit will be presented with 95% confidence intervals based on the MI datasets, as well as the p-value from the JRT for Day 197. The joint rank analysis will only be performed for the mITT population.

The joint rank procedure allows for a statistical test of the treatment effect on the ALSFRS-R total score while accounting for truncation of data due to deaths. In this analysis, a participant's joint rank score will be calculated by comparing each participant to every other participant in the

CONFIDENTIAL

The information contained herein may not be used, disclosed, or published without the written consent of  
Biogen MA Inc.

study, resulting in a score of +1 if the outcome was better than the participant being compared, -1 if worse, and 0 if the same. The participant's score will then be calculated by summing their comparison to all the other participants in the study.

For the purpose of this calculation, participants will be grouped into the following 2 categories:

- Group 1: Participants who complete the study and have data available at the Day 197 assessment AND participants who withdraw from the study due to reasons other than death
- Group 2: Participants who die

MI will be used to impute all missing data before determining the rank score, including intermittent data and data after withdrawal from the study except after death.

In each of the 100 imputed datasets, participants will be ranked as follows:

- Participants in Group 2 will be given lower ranks than participants in Group 1, with the lowest ranks being given to the participants who die in the shortest time after first dose. Progressively higher ranks will be given to participants who die at longer times after first dose.
- Participants in Group 1 will rank higher than participants in Group 2. Progressively higher ranks will be given to participants with a higher change from baseline at Day 197, i.e., a smaller decline at Day 197.

Further details will be described in the statistical analysis plan.

The primary inference will be based on the mITT population. The treatment comparison will be based on a 2-sided  $\alpha$  level of 0.05.

If the second scenario occurs, i.e., in both the active and placebo treatment groups combined the number of participants who died is  $< 3$  (e.g.,  $< 5\%$  deaths out of a total of 60 participants in the mITT population), the primary efficacy analysis will be the change from baseline in ALSFRS-R total score, analyzed using an ANCOVA based on data imputed using MI. The ANCOVA model will include treatment group as a fixed effect and covariates for each of the corresponding baseline value for ALSFRS-R total score, baseline disease duration since symptom onset and use of riluzole or edaravone. The primary inference will be based on the treatment comparison at Week 28. A 2-sided  $\alpha$  level of 0.05 will be used. Treatment differences at other visits will also be presented with nominal p-values.

Sensitivity, supplementary and subgroup analyses of the primary efficacy endpoint will be specified in the statistical analysis plan.

For the non-mITT population, the analysis will be the change from baseline in ALSFRS-R total score, analyzed using an ANCOVA based on data imputed using MI. The ANCOVA model will include treatment group as a fixed effect and covariates for each of the corresponding baseline value for ALSFRS-R total score, baseline disease duration since symptom onset, and use of riluzole or edaravone. Least square means with standard errors will be presented for each treatment group. The difference between treatment groups in least square means for change from baseline at each visit, with corresponding standard errors and 95% confidence intervals, will be presented with nominal p-values.

CONFIDENTIAL

The information contained herein may not be used, disclosed, or published without the written consent of  
Biogen MA Inc.

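### The primary estimand is declared composite with deaths ranked worst, but its variable and summary statistic give death no value, so with 3 or more deaths the reported effect is not the quantity tested

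*Protocol*

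**What the plan says.** All references are to Protocol section 16.2.1.2.1 unless stated.

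- **Population.** "Population: all participants in the mITT population".
- **Variable.** "Variable: change from baseline to Day 197 in the ALSFRS-R total score". Death does not appear.
- **Intercurrent events.** Deaths and withdrawals, under a composite strategy: "participants who have these intercurrent events are ranked against each other and against participants without any intercurrent event using the joint rank methodology". The ranking rules add "Participants in Group 2 will be given lower ranks than participants in Group 1", with earlier deaths ranked lower.
- **Summary.** The "difference between treatment groups in least square means of Day 197 change from baseline", with standard errors and 95% confidence intervals from the ANCOVA on the imputed datasets.
- **Imputation.** For the ranking step: "MI will be used to impute all missing data before determining the rank score". The reach of that rule is then spelled out, and it stops at death: "including intermittent data and data after withdrawal from the study except after death". The statement that the ANCOVA uses multiple imputation is separate and says nothing about death.
- **Two scenarios.** With 3 or more deaths the joint rank test (JRT) gives the primary p-value and the ANCOVA gives the estimates; "The corresponding nominal p-value from the ANCOVA will be presented as a sensitivity analysis". With fewer than 3 deaths the ANCOVA gives both. One estimand text serves both scenarios.
- **Medians.** Differences in median change are also planned, with intervals from the imputed datasets, beside the JRT p-value.

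The latest amendment's rationale for this section explains why test and estimate are separated: the range of the rank score depends on sample size, so the score has no clinical reading.

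**The concern.** Under a composite strategy the event is part of the outcome that is summarised. Here death enters the test, while the variable and summary listed for the same estimand have no place for it. When the JRT is the primary test, its p-value counts mortality but the effect and interval presented as the estimand's summary, as written, do not. A reader could not take the quoted ALSFRS-R difference as the size of what was tested. This is the headline effect of the pivotal part of the study.

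**Working it through.** **Inputs.** Section 16.2.7 gives N = 60, two-sided alpha 0.05, mean slopes of -0.74 (active) and -3.83 (placebo), pooled SD 3.166, Week 28 survival of 90% (active) and 82% (placebo), and 84% power. Assumptions not in the protocol: a 40:20 split (2:1 applied to 60), normal changes, no withdrawals, no covariates. The slope's time unit is not stated, so differences are on the protocol's own slope scale.

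**1. The plan's own figure.** Simulating 20,000 trials, with deaths ranked below all survivors and a t-test on the joint ranks, gives 85.7% power against 84% stated. The figure reproduces within two points.

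**2. How likely is the JRT scenario?** Expected deaths = 40 × 0.10 + 20 × 0.18 = 7.6.
- P(0) = 0.90^40 × 0.82^20 = 0.00028
- P(1) = 0.00247
- P(2) = 0.01069
- P(3 or more) = 1 - 0.0134 = 98.7%

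With milder assumed survival (active/placebo), P(3 or more) is 71% at 95/92, 38% at 97/95 and 16% at 98/97.

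**3. What each quantity responds to.** With death independent of functional change:

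P(better) - P(worse) = sA·sP·w + sA(1 - sP) - sP(1 - sA), where w = 2Φ(3.09 / (3.166·√2)) - 1 = 0.510.

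At 90/82: 0.738 × 0.510 + 0.162 - 0.082 = 0.456.

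| Survival, active/placebo | Mean difference, death given no value | Mean difference, death coded at worst observed change | P(better) - P(worse) |
|---|---|---|---|
| 90% / 82% (protocol) | 3.09 | 3.23 | 0.456 |
| 87.3% / 87.3% (illustrative) | 3.09 | 2.69 | 0.389 |
| 80% / 90% (illustrative) | 3.09 | 1.86 | 0.267 |

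The second column does not move with mortality. When death is instead correlated with decline (latent correlation 0.5 or 0.8), the survivor mean difference moves against mortality. It falls to 2.89 or 2.78 when survival favours active (90/82), and rises to 3.34 or 3.48 when survival favours placebo (80/90).

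**4. Agreement of test and interval.** Planning case, 3 or more deaths, deaths left out of the ANCOVA, latent correlations 0, 0.5 and 0.8:
- 5,000 trials each: the JRT verdict at 0.05 and the interval disagree about zero in 12.6%, 14.1% and 12.3%.
- 8,000 trials each: 12.9%, 13.2% and 12.1%.
- Direction: the interval excludes zero but the JRT is not significant in 8.4-9.1%; the reverse holds in 3.7-5.0%.
- For comparison: 2.6% with no deaths (ranks against means alone), and 4.5-4.7% with deaths coded worst.

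**5. A summary that matches the test.** Let W and L be the active-versus-placebo comparisons won and lost by active. Within-arm comparisons cancel, so the arm difference in mean score is (W - L)/nA + (W - L)/nP = (W - L)·N/(nA·nP). Dividing by N gives (W - L)/(nA·nP), which is exactly P(better) - P(worse). As a check, the simulated mean rank difference was 13.72; a score difference is twice a rank difference, and 2 × 13.72 / 60 = 0.457, against 0.456 above.

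**The case against.** **The split is deliberate.** This stands as far as it goes. The protocol discloses that the test and the estimate come from different analyses and gives its reason. The reason supports a points-scale estimate. It does not explain how death enters that estimate, or why a mean without death is listed as the summary of a composite estimand. Dividing by N answers the sample-size objection, though the result is still not in ALSFRS-R points.

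**The SAP may settle it.** The section defers further detail to the SAP, which could code death as a worst score. That is why survivor-only estimation cannot be asserted as the plan. A reader might infer it from the imputation rule that stops at death, but that rule is written for the ranking step, and the ANCOVA's own imputation statement has no such exception. If values after death were imputed, the estimate would be hypothetical, which is not composite either. The conflict lies among attributes that the protocol itself fixes.

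**A median difference is already planned.** A median can place deaths at the bottom without scoring them. The protocol does not say that it will, so the gap stays open.

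**A rank summary would misfit the fewer-than-3-deaths scenario.** Correct. There the ANCOVA is the primary test, so the rank summary must be limited to 3 or more deaths.

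**The practical effect is small.** Partly so. Most of the disagreements are an interval excluding zero beside a non-significant JRT, and the JRT governs. In about 9,900 planning-case trials no significant JRT stood beside an estimate of opposite sign. The ANCOVA p-value is shown as a sensitivity analysis, and mortality is reported in the time-to-event endpoints.

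**Conclusion.** The point holds as an inconsistency within the stated estimand. Handling of death is composite; the variable and summary, as written, are not, and would become so only if death were coded as a worst outcome. At the protocol's survival assumptions the affected scenario is close to certain (98.7%), but its likelihood depends on survival (16-71% under the milder values tried). The 12-14% disagreement holds only if deaths are left out of the ANCOVA, and rests on the 40:20 split, normality, no covariates and no withdrawals.

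A reader might infer more than the documents support:
- That the JRT, its type I error, its power or N is compromised. None is affected.
- That the same contradiction exists for SVC. Section 16.2.1.2.2 declares no estimand there.
- That labelling withdrawals composite changes the analysis. They are ranked on imputed values and what will be done is clear; only the term is wrong.

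The weight is minor to moderate, limited to reporting and interpretation. It is worth fixing because it concerns the headline effect size and costs little.

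**What to change.** In section 16.2.1.2.1:

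1. For 3 or more deaths only, word the variable as the joint rank of death and ALSFRS-R change. Name as its summary the joint-rank score difference divided by N, with 95% confidence interval. Describe the covariate-adjusted version, a rescaling of the planned ANCOVA and PROC MIANALYZE output, as the adjusted analogue of P(better) - P(worse). Its interval agrees with the JRT p-value by construction.
2. Keep the ANCOVA difference in points beside it for clinical reading, labelled as a separate non-composite estimand (survivor or hypothetical), and state how deaths are handled. State whether the planned median difference places deaths at the bottom.
3. For fewer than 3 deaths, keep the least-squares mean difference as both test and estimate, and say that its estimand is not the joint-rank composite.
4. Describe withdrawals as handled by imputation.

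The cost is wording plus one rescaled statistic. The test, alpha, power, N and the 3-death rule stay as they are.
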